
For non-clinical questions (i.e., unrelated to patient eligibility, treatment, or clinical data submission) contact the CTSU Help Desk by phone or email: CTSU General Information Line – [REDACTED] All calls and correspondence will be triaged to the appropriate CTSU representative.
		

RT CHARM: PHASE III RANDOMIZED TRIAL OF HYPOFRACTIONATED POST MASTECTOMY RADIATION WITH BREAST RECONSTRUCTION

Eligibility Criteria (see [Section 3.2](#))

Required Initial Laboratory Values

None

Histologically confirmed invasive carcinoma of the breast. (See [§3.2.1](#))

Pathologic stage T0N1-2a, T1N1-2a, T2N1-2a, T3N0-2a, all M0 status. (See [§3.2.2](#))

No prior therapeutic radiation therapy to the chest, neck or axilla. (See [§3.2.3](#))

No prior history of ipsilateral breast cancer (invasive disease or DCIS). (See [§3.2.4](#))

No history of prior or concurrent contralateral invasive breast cancer. (See [§3.2.5](#))

No active collagen vascular diseases, such as: systemic lupus erythematosus, scleroderma, or dermatomyositis.

Negative inked histologic margins from mastectomy pathology. (See [§3.2.7](#))

No significant post mastectomy complications requiring an unplanned re-operation, or admission for IV antibiotics. (See [§3.2.8](#))

Intent to meet dose constraints. (See [§3.2.9](#))

Radiation oncologist is planning to treat regional lymph nodes including internal mammary nodes.

Radiation oncologist is NOT planning to utilize a chest wall/scar boost.

Patient has undergone breast reconstruction or is planning to undergo reconstruction.

Plan to start radiation treatment within the timeframes specified in [Section 7.0](#)

If using tissue expander, no air expander, only fluid filled expanders (See [§3.2.13](#))

For patients with diabetes, hemoglobin A1C test must have been performed ≤ 90 days prior to registration.

No co-existing medical conditions with life expectancy < 5 years.

No other malignancy within 5 years of registration with exception of basal cell or squamous cell carcinoma of the skin. (See [§3.2.17](#))

Negative serum or urine HCG in women of child-bearing potential ≤ 7 days prior to registration (See [§3.2.18](#))

[figure not shown]
Women of child-bearing potential must agree to utilize a form of birth control or agree to undergo sexual abstinence during radiation therapy.

ECOG (Zubrod) Performance Status 0-1

Patient ≥ 18 years of age

Patients must be able to read and comprehend English, except French patients from CCTG institutions. (See [§ 3.2.22](#))

Schema

* Regional Nodes will include axilla (Levels I, II, III), supraclavicular fossa and internal mammary nodes. If an axillary dissection has been performed, RT will only be directed to the un-dissected axilla.

** Patients will be stratified before randomization for immediate versus delayed and autologous versus implant only reconstruction. All reconstruction must be completed before radiation to be classified as immediate and autologous reconstruction is autologous tissue +/- implant.

All patients will undergo reconstruction of the breast; either before or after radiation, but it must be completed within 18 months after finishing radiation therapy, unless medically contraindicated.

Patients will be followed until 15 years after completion of radiation therapy or until death, whichever comes first ([§11.3](#))

Please refer to the full protocol text for a complete description of the eligibility criteria and treatment plan.

There is no surgical credentialing required for participation on this study.

Radiation therapy requires credentialing and submission of patient plans for review. See Sections [7.5](#) and [14.0](#) for more detail.

Table of Contents

Section	Page
1.0 BACKGROUND	8
1.1 Rationale for the Study	8
1.2 Baseline Toxicity from PMRT.....	9
1.3 Altered Fractionation in Breast Cancer.....	11
1.4 Patient Satisfaction and Well-being as Patient Reported Outcomes (PROs).....	12
1.5 Photographic Cosmetic Assessment	14
1.6 Study Hypotheses	14
2.0 OBJECTIVES	14
2.1 Primary Objective	14
2.2 Secondary Objectives.....	14
2.3 Photographic Cosmetic Assessment	15
2.4 Lymphedema Assessment.....	15
2.5 Patient Reported Outcomes (PRO) Objectives	15
2.6 Economic Analysis	15
2.7 Correlative Science Objectives	15
3.0 PATIENT SELECTION.....	16
3.1 On-Study Guidelines.....	16
3.2 Eligibility Criteria	17
4.0 PATIENT REGISTRATION.....	19
4.1 Investigator and Research Associate registration with CTEP.....	19
4.2 CTSU Site Registration Procedures	20
4.3 Patient Registration Requirements.....	22
4.4 Patient Registration/Randomization Procedures.....	22
4.5 Registration to Correlative and Companion Studies.....	23
4.6 Stratification Factors and Treatment Assignments	23
5.0 STUDY CALENDAR.....	25
6.0 DATA AND SPECIMEN SUBMISSION.....	26
6.1 Data Collection and Submission	26
6.2 Specimen collection and submission	28

1.0 BACKGROUND

In the last 5-10 years, there has been a significant shift in the radiation of women with intact breast cancer to shorter, more cost effective and convenient treatment courses. Through the work of several prospective published trials, this concept has been found to be safe and effective in women undergoing breast conserving therapy.[1-4] Decreasing the time required for women to undergo post mastectomy radiation decreases health care costs, and allows patients to spend more time out side of the healthcare setting, ultimately improving patient, employer and payer satisfaction. As the outcomes with traditional post mastectomy are already considered safe and effective, this trial is designed as a non-inferiority trial to ensure that a shorter time course of radiation is as safe as the current standard of care. Although there are limited data from Europe that support this concept in mastectomy and regional nodal irradiation (RNI) patients, no studies have been done in the setting of breast reconstruction. We need prospective randomized data using modern radiotherapy and chemotherapy before widespread adoption occurs here in the United States and elsewhere. Post Mastectomy Radiation Therapy (PMRT) in this setting is a combination of all hypofractionation challenges, combining concerns over adjuvant chemotherapy, post mastectomy chest wall, supraclavicular fossa, internal mammary nodes and reconstructed breast short course radiation. Each of these factors independently is a potential contraindication to hypofractionated radiation due to a lack of data. There are two pressing and currently outstanding questions related to hypofractionation that require resolution in a phase III setting:

- 1) What is the rate of radiation related complications in reconstructed chest walls treated with shortened course radiotherapy?
- 2) Is hypofractionation safe when treating regional nodal volumes (where the brachial plexus is located)?

These two questions have been contentious, and their uncertainty will directly affect patient care for years to come, unless a well-designed study can define the unknowns. In this study, both of these questions will be tested and resolved as primary and secondary endpoints. This trial design also collects much needed prospective data regarding the true complication rates for PMRT with breast reconstruction, given the multitude of options for breast reconstruction timing and techniques.

1.1 Rationale for the Study

The primary rationale for accelerated PMRT is the enhanced convenience for patients, which may result in increased access to PMRT. With data now available documenting the low alpha/beta ratio for breast cancer, the fraction sensitivity of breast cancer can be exploited with higher fraction sizes, resulting in more compressed treatment times. We will deliver a dose of 42.56 Gy to the chest wall/reconstructed breast and regional nodes, in 16 daily fractions, 5 days a week. This fractionation should produce late effects and tumor control comparable to a conventionally fractionated course of 50 Gy to the chest wall and regional lymph nodes delivered in 2 Gy daily fractions. No chest wall or reconstructed breast boost will be allowed on this trial. This fractionation scheme has the benefit of delivering the entire treatment over 16 treatment days (weekdays only). This fractionation scheme closely matches that used for breast conservation in the Ontario Clinical Oncology Group and UK Start B trial, as well as the recently closed NRG/ROG 1005. [2, 3, 5]

As the majority of the radiation oncology community believes that such a fractionation is likely to be equally effective, the key question is that of adverse events, especially in the setting of breast reconstruction. One of the primary supporting trials for this concept is the UK Start B trial. [2] The UK Start B was an accelerated hypofractionation trial comparing 50Gy in 2Gy daily fractions for 5 weeks versus 40Gy delivered in 2.67Gy daily for 15 days. This trial accrued 2215 stage I and II breast cancer patients between 1999 and 2001. Pertinent patient factors in this trial include the fact that 7% of the patients were radiated after mastectomy, 7% received hypofractionated regional nodal radiation and 23% received chemotherapy with or without tamoxifen. The 10 year analysis of this trial demonstrates equivalent local control with local relapse (LR) rate of 5.5% in the 50Gy arm and 4.3% in the 40Gy arm (p=0.21). None of the patients treated in either arm had any reported brachial plexopathy. The UK Start A trial was a precursor trial to Start B, and randomized 2236 early stage breast cancer patients to 50Gy in 25 fractions versus 39Gy or 41.6Gy in 13 fractions over 5 weeks. Contrary to popular conception of

hypofractionation, the 2013 combined analysis of Start A and B demonstrates the late effect to be statistically better in the hypofractionated radiation arms. [5] In the Start A 39Gy arm, moderate or marked breast induration, telangiectasia, and breast edema were significantly less common than the 50Gy arm. In the Start B 40Gy arm, breast shrinkage, telangiectasia, and breast edema were less common than in the 50Gy arm. Given the low adverse event rate of PMRT on the non-reconstructed chest wall, a large sample size would be required to demonstrate superiority (see baseline toxicity). Therefore, we have selected a more frequently seen toxicity in evaluating reconstruction complications to demonstrate non-inferiority of hypofractionation. This method will require significantly fewer participants.

The efficacy of irradiating the chest wall and draining lymph nodes after mastectomy for an improvement in locoregional control has been firmly established by multiple older trials comparing mastectomy alone to mastectomy with postoperative radiation [6-12]. These trials typically used outdated radiation techniques and equipment that produced orthovoltage x-rays. Several trials have studied the efficacy and added benefit of PMRT in the presence of systemic therapy [13-25]. The most definitive of these have come from the Danish Breast Cancer Cooperative Group [21, 22] and the British Columbia Cancer Agency [23]. In addition to these, the updated findings of the Early Breast Cancer Trialists Collaborative Group (EBCTCG) meta-analysis [26, 27], have decisively altered practice and reaffirmed the role of PMRT in modern breast oncology.

The British Columbia trial enrolled 318 node-positive premenopausal breast cancer patients and randomized them after modified radical mastectomy to either radiation therapy or no additional locoregional therapy [23]. Both groups received adjuvant CMF chemotherapy for 12 (first 80 patients) or 6 months. Radiation therapy was hypofractionated and delivered to the chest wall to a dose of 37.5 Gy in 16 daily fractions through opposed tangential photon fields. After a median follow-up of 20 years, the 20-year survival free of locoregional disease developing before systemic was 61% in the chemotherapy alone arm and 87% in the irradiated group. The irradiated group had significantly higher 20-year event-free survival (38% vs. 25%), systemic disease-free survival (48% vs. 31%), breast-cancer specific survival (53% vs. 38%), and overall survival (47% vs. 37%). There were 3 cardiac deaths (2%) in the irradiated group versus one (0.6%) in the control group ($p=0.62$), and 9% of patients in the irradiated group developed arm edema compared with 3% in the control group ($p=0.035$).

The Early Breast Cancer Trialists' Collaborative Group has collected primary data from every randomized trial of adjuvant radiotherapy in breast cancer, and periodically reports the ongoing analyses on the benefits and risks of radiation therapy in these patients. The most recent report from 2005 reviewed data on 9933 patients enrolled on 25 trials of PMRT, all of which were not confounded by the use of systemic therapy [26]. Node-positive patients who had axillary clearance and received radiation therapy after mastectomy had a 5-year locoregional recurrence rate of 6%, compared to 23% for non-irradiated controls (15-year rates were 8% vs. 29%). In a recent 2014 update to the EBCTCG data, PMRT was again evaluated and in all node positive patients found to result in improved local control and disease free survival. [27] In particular, N1 patients the addition of PMRT was found to decrease the 10 yr. local recurrence from 20% to 4% ($p<0.0001$) and improve the 20 yr. breast cancer mortality from 50% to 42% ($p=0.01$).

1.2 Baseline Toxicity from PMRT

In reviewing toxicity data from previous PMRT trials, the Vancouver BC trial reported 9% arm lymphedema (4% needing intervention) and 0.6% symptomatic pulmonary fibrosis. [23]. There was no assessment of cosmesis or reconstruction complications reported in the Danish or Vancouver BC PMRT trials, or the PMRT participants of the UK Start trials. Although not a trial looking at mastectomy patients, the NCIC MA.20, revealed a 7% risk of grade 2 or greater lymphedema in the regional nodal radiation group treated with standard fractionation. [28] With approximately 25% of the Start trial patients undergoing mastectomy, the 5 yr. toxicity data from the hypofractionation arm of 40Gy in 15 fractions in the Start B trial reported the following:

Symptomatic rib fracture	2%
Lung fibrosis	1.7%
Ischemic heart disease	1.5%
Brachial plexopathy	0%
Breast edema	5%
Telangiectasia	1.8%
Arm stiffness	3%
Arm Lymphedema	3%

Based on this information, we feel that a reasonable expected combined grade 2 or greater non-acute toxicity rate would be 7-10%, a conservative estimate as many trials (including NCIC MA.20) have concluded that the risk of grade 2 lymphedema alone to be at least this high with regional nodal RT. In the next section, the 2014 updated analysis of Start A and B is discussed with results suggesting that toxicity from hypofractionation may actually be superior to conventional fractionation.

Research has found that PMRT is an independent risk factor for complications in patients undergoing breast reconstruction. Radiation-associated complications include infection, seroma, delayed wound healing, capsular contracture, implant removal, fat necrosis and poor cosmetic results. A recently published claims-based review evaluated the complications for 14,894 reconstructed patients with an average age of 54. [29] They found a rate of 5-10% wound healing difficulty, 20% infection, 25% implant removal and 16% fat necrosis (autologous). These numbers included patients undergoing both implant and autologous reconstruction, with and without radiation therapy (RT), and RT was associated with an increased risk of infection, implant removal and fat necrosis. To ensure a sufficient event rate, we've selected a conservative composite reconstruction event rate of 25% in our standard treatment arm. Reflecting the heterogeneity of breast reconstruction practiced in the country, in this trial we plan to allow a variety of reconstruction techniques, given the controversy over superiority in the literature: immediate or delayed implants, autologous tissue, or a combination of both. We also plan to allow the use of acellular dermal matrix or similar soft tissue augmentation matrices.

Benediktsson et al. 2006[30]	107 pts. PMRT & Immediate reconstruction, saline prosthesis	41.7% Baker 3 or 4 contracture	
Christante, et al. 2010[31]	100 pts. PMRT & Immediate breast reconstruction	44% complications and 31% required implant removal	Delayed reconstruction patients had only a 22% complication rate
Cordeiro et al. 2004[32]	159 pts. Recon before RT	68% contracture with 80% patient good cosmesis	
Alderman, et al. 2002[33]	326 pts. PMRT, 12 centers	52% complications in immediate reconstruction	Delayed reconstruction rate 33%
Whitfield, et al. 2008[34]	42 pts. PMRT implants or TEs, 40Gy in 15 fractions	19.5% revisional surgery for capsular contracture	
Jhaveri, et al. 2008[35]	92 pts. PMRT and Immediate recon	25% rate of severe complications (Surgery or IV antibiotics)	0% complication autologous tissue recon
Fowble, et al. 2015[36]	99 pts. Immed TE and PMRT	18% failure rate 3.8 yrs.	

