12.3.2 Analysis Plan for Primary Endpoint

The null hypothesis for our primary analysis is that the proportion of patients who experience a breast reconstruction complication within two years after the end of radiation treatment on Arm 2 (hypofractionated dosing) (denoted π_2) will be at least 0.1 higher than the proportion of patients in Arm 1 (denoted π_1) (standard dosing) (i.e. that hypofractionated dosing is inferior to standard dosing). This will be tested using a two-sample test of proportions. In particular, we will calculate the test statistic: $Z = (\pi_1 - \pi_2 + 0.1) / [\pi_1(1 - \pi_1)/n_1 + \pi_2(1 - \pi_2)/n_2]^{1/2}$, where n_1 and n_2 are the numbers of patients in Arms 1 and 2, respectively.

Interim analysis decision rule

Interim analysis of inferiority of hypofractionated PMRT (futility) as compared to conventional PMRT will be conducted when 30% of patients are enrolled and have reached two years post-radiation. The Lan-DeMets family of alpha and beta spending functions corresponding to the O'Brien-Fleming boundary are used for controlling overall type II error rates. Inferiority of the hypofractionated PMRT will be concluded if $p\text{-value} > 0.843$ (corresponding to $Z < -1.007$). The second stage of this clinical trial shall continue if $p\text{-value} \leq 0.843$.

Final analysis decision rule

Final analysis will be conducted when all target patients are enrolled and have reached 2 years post radiation. Non-inferiority of hypofractionated PMRT will be concluded if $p\text{-value} < .025$ (corresponding to $Z > 1.96$) and inferiority of hypofractionated PMRT will be concluded if $p\text{-value} \geq .025$ (corresponding to $Z \leq 1.96$).

Study Operating characteristics

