12.4 Supplementary/Secondary Analysis Plans

12.4.1 Secondary Objectives

Incidence of acute and late radiation complications based on CTCAE 4.0 toxicity. The proportion of patients with acute or late radiation complications, will be estimated separately by treatment arm and will be compared across the two arms using two-sample test of proportions (Z test) with a two-sided alternative.

Local and local regional recurrence rate: The cumulative incidence of local and local regional recurrence will be estimated separately by treatment arm using the cumulative incidence function treating death as the competing risk and will be compared using Gray's test. In addition, local and local regional recurrence free survival will be summarized for each arm using the Kaplan-Meier estimators, and will be compared using a log rank test.

Reconstruction complication rates based on reconstruction method (autologous +/- implant vs. implant only) and timing of reconstruction received (immediate vs. intent for delayed): Between-arm differences in reconstruction complication rates will be assessed separately within each of the six subgroups based on type and timing of reconstruction. Between-arm differences in complication rates will also be assessed within the two broader subgroups of patients who receive implant only and those who receive autologous based reconstruction. Within each subgroup, the comparison will be done using a two-sample Z test of proportions with a two-sided alternative as described for the primary analysis in Section 12.3.2.

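### The subgroup comparisons in Section 12.4.1 reuse an unpooled Z statistic that is undefined at 0 v 0 events and unreliable when events are few, and no sparse-data method is given

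*Combined protocol and SAP*

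**What the plan says.** Section 12.4.1 serves objective 2.2.3. It says that between-arm differences in complication rates "will be assessed separately within each of the six subgroups based on type and timing of reconstruction", and then within two broader groups (implant only, autologous based). The test in each is made "using a two-sample Z test of proportions with a two-sided alternative as described for the primary analysis in Section 12.3.2".

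Section 12.3.2 contains one formula. It is introduced by "This will be tested using a two-sample test of proportions. In particular, we will calculate the test statistic" and reads Z = (π1 − π2 + 0.1) / √[π1(1 − π1)/n1 + π2(1 − π2)/n2]. The 0.1 is the margin in the primary null hypothesis, under which the Arm 2 rate "will be at least 0.1 higher than the proportion of patients in Arm 1". The rule beginning "Non-inferiority of hypofractionated PMRT will be concluded if" (Z > 1.96) is given for the final primary analysis only.

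The plan gives no subgroup sizes, no complication rate by reconstruction type, no decision rule for subgroups and no method for sparse tables. The only planning rate is 25% for the control arm (Section 12.2). The literature table in Section 1.2 has one autologous-specific complication entry, "0% complication autologous tissue recon", beside a 92-patient series of immediate reconstruction.

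**The concern.** The unpooled variance is adequate at 396 per arm and a 25% rate. Six subgroups, some of them possibly small and with low event rates, are a different setting. With no events in either arm the estimated variance is zero. With one event it rests on a single patient and is too small.

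Objective 2.2.3 asks how complication rates compare by method and timing of reconstruction. In a sparse subgroup the planned test may produce nothing. If the 0.1 term is carried over, it may instead produce a large Z from very little information. An analyst would then have to choose a method after seeing the tables.

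**Working it through.** **1. The plan's own figure.** Inputs from Section 12.2: 25% in both arms, margin 0.10, one-sided alpha 0.025, power 90%. n per arm = (1.960 + 1.282)² × 2 × 0.25 × 0.75 / 0.10² = 394.0, so 395 against the stated 396. Then 792 / 0.90 = 880, as stated. Power at 396 per arm is 90.1%, and 80.4% at a 50% control rate (stated: about 80%). The formula works at the scale of the primary analysis.

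**2. Assumed subgroup sizes.** The plan gives none. An even split is 792 / 6 / 2 = 66 per arm. A subgroup of 60 patients, 30 per arm, illustrates a smaller one.

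**3. No events in either arm.** The denominator is √0 = 0. With the shift Z = 0.1/0; without it Z = 0/0. Neither is a number. At a common true rate p with m patients per arm, the chance of this table is (1 − p)^(2m):

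| True rate | 30 per arm | 66 per arm |
|---|---|---|
| 1% | 54.7% | 26.5% |
| 3% | 16.1% | 1.8% |
| 5% | 4.6% | 0.1% |
| 10% | 0.2% | about 0 |

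**4. One event.** Take 0/30 in Arm 1 and 1/30 in Arm 2, with the shift.
- Numerator: 0 − 0.0333 + 0.1 = 0.0667.
- Unpooled standard error: √(0.0333 × 0.9667 / 30) = 0.0328, so Z = 2.03, above 1.96.
- Score test: under a 10-point difference the restricted estimates are 0 and 0.1. The Miettinen-Nurminen standard error is √(0.1 × 0.9 / 30 × 60/59) = 0.0552, so Z = 1.21.

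**5. One-sided error on the margin.** Exact enumeration of both binomials: probability that the unpooled Z with the shift exceeds 1.96 when Arm 2 is truly 10 points worse. Tables with zero variance are not counted as passes. Nominal is 2.5%.

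| True rates | 30 per arm | 66 per arm |
|---|---|---|
| 1% v 11% | 12.0% | 6.1% |
| 3% v 13% | 8.0% | 3.8% |
| 10% v 20% | 3.2% | 3.1% |
| 25% v 35% | 2.8% | 2.7% |

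The Miettinen-Nurminen score test at 30 per arm gives 0.8% (1% v 11%) and 1.4% (3% v 13%). At 10 and 20 per arm the unpooled result depends mostly on how 0 v 0 is treated: for 1% v 11% at 20 per arm it is 1.8% if not counted as a pass and 9.8% if counted. No conclusion here rests on those sizes.

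**6. Why the shift must be settled.** At equal true rates of 5% and 66 per arm, a two-sided test that keeps the 0.1 term has |Z| > 1.96 in 73.5% of trials, against 6.2% without it. Without the shift the unpooled test is still erratic: at equal rates it rejects in 0.4% of trials at 2% and 33 per arm, and in 9.4% at 25% and 10 per arm.

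**The case against.** A reader might infer that the protocol expects no complications after autologous reconstruction, so that 0 v 0 tables are likely. The documents do not support that. The 0% is one entry in a background table. It sits beside a rate of severe complications, those needing surgery or intravenous antibiotics, whereas Section 10.1 also counts Baker III-IV contracture and any unplanned reconstruction-related admission, including for pain. The number of autologous patients is not given, and a zero count can be weak evidence: the exact 97.5% upper limit, 1 − 0.025^(1/k), is 31% for 0/10 and 17% for 0/20. Section 1.2 also reports 16% fat necrosis in autologous cases. That is not itself an endpoint event, and the source mixes irradiated and unirradiated patients, but it does not suggest freedom from problems. A low rate is plausible and no more.

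A reader might also infer that 0 v 0 gives automatic non-inferiority. It does not: 0.1/0 is undefined, 12.4.1 specifies a two-sided alternative, and no subgroup non-inferiority rule exists.

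It can fairly be added that these are secondary comparisons, that the two broader subgroups reduce sparsity, and that many analysts would move to an exact or score method unprompted. All of this stands and limits the importance of the point. It does not remove the gap, because the plan names a specific formula and says nothing about when to leave it.

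**Conclusion.** The point holds as a minor defect in a secondary analysis. The statistic named for the subgroups fails at 0 v 0 under either reading. With the shift kept, it also understates uncertainty when events are few.

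The size depends on assumptions that the plan does not settle. At control rates of 1% to 3%, the one-sided error is 8.0% to 12.0% at 30 per arm and 3.8% to 6.1% at 66 per arm, against 2.5%. At control rates of 10% or more it is about 3% at both sizes, which is of little consequence. These figures assume that the shift is retained and that Z > 1.96 would be read as in the primary analysis. If the two-sided wording means an ordinary difference test, they do not apply; what remains is a missing result at 0 v 0 and poor small-sample behaviour. The primary analysis, the design and the sample size are unaffected.

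**What to change.** In Section 12.4.1, replace the subgroup Z test with the Miettinen-Nurminen score confidence interval and test for the risk difference. State in the same sentence whether the 0.1 shift applies; a two-sided alternative implies that it does not.

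Let the interval lead the report. It remains defined with no events: at 0/m v 0/m the 95% limits are ±k/(m + k), with k = 3.84 × 2m/(2m − 1). At 30 per arm k = 3.91, giving ±11.5 points; at 66 per arm k = 3.87, giving ±5.5 points. A score test of zero difference is itself 0/0 at no events, so add that such a table is reported as showing no evidence of a difference (p = 1).

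The cost is a line or two in the plan and a standard software option. In large subgroups the result agrees with the planned test. The small downside is wider intervals in sparse subgroups, which reflect the information actually there. The change should be made before subgroup results by arm are seen.
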